7.2.5. Exploratory Endpoints

[figure not shown]
The exploratory endpoints of this study are:

- Change from baseline in eGFR over time
- Change from baseline in 24-hour UPE over time
- Change from baseline in 24-hour uPCR over time
- Change from baseline in uACR (from spot urine) over time
- Change from baseline in 24-hour uACR over time
- Achievement of $\geq 50\%$ reduction from baseline in 24-hour UPE at any time post baseline
- Achievement of $\geq 30\%$ reduction from baseline in 24-hour UPE at any time post baseline
- Duration of treatment response defined as the number of weeks between the first timepoint at which the patient achieves a $\geq 30\%$ reduction from baseline in 24-hour UPE and the first timepoint at which the patient relapses (a relapse is defined as an increase in 24-hour UPE by $\geq 30\%$ from the value of the lowest measured post-treatment UPE in a patient whose 24-hour UPE is > 1 g)
- Achievement of 24-hour UPE of < 0.3 g at 36 weeks (complete proteinuria remission)
- Duration of complete proteinuria remission defined as the number of consecutive weeks with UPE < 0.3 g/day from the first timepoint at which UPE < 0.3 g/day to the first timepoint at which UPE ≥ 0.3 g/day
- Duration of partial proteinuria remission defined as the number of consecutive weeks with UPE < 0.6 g/day from the first timepoint at which UPE < 0.6 g/day to the first timepoint at which UPE ≥ 0.6 g/day

CONFIDENTIAL

No use, disclosure, or reproduction outside of Omertos without prior written authorization

- 24-hour UPE following narsoplimab retreatment in patients who relapse after treatment
- Change from baseline in the number of red blood cells per high-powered field (RBC/HPF) over time from baseline

8. SELECTION AND WITHDRAWAL OF PATIENTS

The inclusion and exclusion criteria will be assessed during the Screening and Run-In periods, and only those patients who continue to meet all the inclusion criteria and who do not meet any of the exclusion criteria will be eligible to continue into the Initial Treatment period.

8.1. Patient Inclusion Criteria

Patients may be included in the study only if they meet all the following criteria during the Screening Period and Run-In Period:

1. Age 18 years or older at the onset of Screening
2. Understand and voluntarily sign an informed consent form in accordance with regulations and governing institutional review board (IRB) or independent ethics committee (IEC) requirements prior to any procedures or evaluations performed specifically for the sole purpose of the study
3. Biopsy-confirmed diagnosis of IgAN within 8 years prior to Screening or Run-In Visit 1
4. Documented history of proteinuria > 1 g/day within 6 months prior to Screening, or uPCR > 0.75 by spot urine, at Screening
5. Mean of two proteinuria measurements > 1 g/day at baseline

CONFIDENTIAL

No use, disclosure, or reproduction outside of Omertos without prior written authorization

6. Estimated glomerular filtration rate of ≥ 30 mL/min/1.73 m² calculated according to the Chronic Kidney Disease Epidemiology Collaboration (CKD-EPI) equation [[Levey 2009](#)] at Screening and baseline
7. Females should either a) not be of childbearing potential (i.e., surgically sterilized or postmenopausal for > 1 year), b) have a negative pregnancy test at Screening and baseline and, irrespective of sexual activity, must agree to use two medically reliable forms of contraception from study entry, throughout the study, and for at least 12 weeks after the last dose of study drug, including possible retreatments, or c) have a medically sterilized male partner. Acceptable methods of contraception include a reliable intrauterine device, hormonal contraception, a barrier method, or complete abstinence (periodic abstinence [e.g., calendar, ovulation, symptothermal, post-ovulation methods] and withdrawal are not acceptable methods of contraception).
8. Males should either a) not be of reproductive potential or b) irrespective of sexual activity, must agree to use a medically reliable form of contraception from study entry, throughout the study, and for at least 12 weeks after the last dose of study drug, including possible retreatments. Acceptable methods of birth control include spermicide in combination with a barrier method, complete abstinence (periodic abstinence [e.g., calendar, ovulation, symptothermal, post-ovulation methods] and withdrawal are not acceptable methods of contraception), or patient's female partner is willing to use medically acceptable methods of birth control (i.e., intrauterine device, hormonal contraception, or a barrier method).
9. Male patients must be willing to avoid fathering children for at least 12 weeks following the last dose of study medication

8.2. Patient Exclusion Criteria

Patients will be excluded from the study for any of the following reasons:

1. Treatment with immunosuppressants (e.g., azathioprine or cyclophosphamide), or Chinese Traditional Medicine with immunosuppressive function, cytotoxic drugs, for IgAN within 8 weeks prior to Screening. Treatment with immunosuppressants, Chinese Traditional Medicine with immunosuppressive function, or cytotoxic drugs for IgAN is not allowed during the Run-In Period. Treatment with immunosuppressants are allowed if such treatment is for indications other than IgAN.
2. Treatment with eculizumab within 8 weeks prior to Screening. Treatment with eculizumab is not allowed during the Run-In Period.
3. Treatment with systemic corticosteroids within 8 weeks prior to Screening. Treatment with systemic corticosteroids is not allowed during the Run-In Period.
4. Uncontrolled BP, a systolic BP of > 150 mmHg and a diastolic BP of > 100 mmHg at rest despite the combination of two or more anti-hypertensives including ACEIs, ARBs, or direct renin inhibitors at Screening and baseline
5. Female patients who are pregnant, breast feeding, or planning to become pregnant until 12 weeks after the last dose of study drug, including possible retreatments. Males who are

CONFIDENTIAL

No use, disclosure, or reproduction outside of Omertos without prior written authorization

planning to father children up through 12 weeks after the last dose of study drug, including possible retreatments.

6. Clinical or biological evidence of Type 1 diabetes mellitus (DM) or poorly controlled DM with hemoglobin A1c > 7.5 or with evidence of diabetic nephropathy on biopsy, systemic lupus erythematosus, IgA vasculitis (Henoch-Schonlein purpura), secondary IgAN, or other renal disease during Screening and Run-In
7. Presence of significant morbidity or other major illness or disease that may confound the interpretation of the clinical trial results or may result in death within 2 years of Screening
8. History of renal transplantation
9. Have a known hypersensitivity to any constituent of the investigational product
10. Rapidly progressive glomerulonephritis, defined as a fall in eGFR of > 30 mL/min/1.73 m² within 24 weeks or > 15 mL/min/1.73 m² within 12 weeks of Screening. During the Run-In period a patient will be excluded if they experience a decrease in eGFR of > 15 mL/min/1.73 m² from their best eGFR from the beginning of Screening.
11. Significant abnormalities in clinical laboratory values including any of the following at the time of evaluation during Screening and Run-In:
 - > hemoglobin < 9.0 g/dL
 - > platelet count < 100,000 cells/mm³
 - > absolute neutrophil count < 500 cells/mm³
 - > alanine transaminase or aspartate transaminase (AST) > 3.0 × the upper limit of normal (ULN)
 - > serum bilirubin > 2 × ULN
12. History of HIV, evidence of immune suppression, active HCV infection (patients with positive anti-HCV antibody but a non-detected HCV RNA PCR can enroll), and/or HBV infection (patients with positive HBsAg are excluded; for patients with isolated positive anti-HBc antibody, HBV DNA test by PCR must be non-detectable to enroll).
13. Diagnosis of a malignancy except for adequately treated and cured basal or squamous cell skin cancer, curatively treated *in situ* disease, or other cancer from which the patient has been disease-free for ≥ 5 years
14. Have received any other investigational drug or device or experimental procedures within 30 days of the Screening Visit or within 5 times the plasma half-life of the administered experimental drug, whichever is longer
15. Previously received narsoplimab¹

¹ Patients currently participating in OMS721-IGA-001 whose study treatment was interrupted due to the COVID-19 pandemic may resume or reinitiate study treatment once it is allowed by their institution. See Section 10.2, Study Schedule, for specific guidance on resumption of study treatment.

CONFIDENTIAL

No use, disclosure, or reproduction outside of Omersa without prior written authorization

16. Is an employee of Omeros, the investigative site (whereas site is meant as the clinic, department, or Clinical Research Unit in which the Investigator works or conducts the trial), a study staff member, or their immediate family member
17. Presence of any condition that the Investigator believes would put the patient at risk from participation
18. Any patient who, in the opinion of the Investigator, is likely to be noncompliant or who is not suitable for the study
19. Presence of active infection occurring within 7 days of Screening or at the time of Screening
20. Treatment with or change in dosing of sodium glucose co-transporter 2 inhibitors (SGLT2i) during Screening and Run-In Periods. However, a stable dose regimen established at least 8 weeks prior to screening is acceptable.
21. Treatment with Tarpeyo™ (budesonide) or other approved treatments for IgAN within 6 months prior to screening. Treatment with Tarpeyo™ is not allowed during Screening and Run-In Periods or any time throughout the study.
22. Treatment with Kerendia® (finnerenone) within 6 months prior to screening. Treatment with Kerendia® is not allowed during Screening and Run-In Periods.
23. Initiation of treatment with Filspari™ (sparsentan), a dual Endothelin Angiotensin Receptor Antagonist (dEARA) or similar medication within three months prior to screening. A stable dose initiated at minimum 3 months before screening is acceptable and will take the place of ACEi/ARB as background therapy.

8.3. Patient Withdrawal Criteria

Patients may voluntarily withdraw from receipt of study drug or from the study at any time for any reason without prejudice to further treatment.

8.3.1. Early Discontinuation of Study Drug

A patient must permanently discontinue study drug under any of the following circumstances:

- The patient becomes pregnant. Study drug must be discontinued immediately, and the pregnancy reported to the Sponsor.
- The patient wishes to discontinue study drug treatment for any reason.
- The patient experiences a medical emergency that necessitates discontinuing study drug treatment.
- The Investigator, Sponsor, or patient's primary care provider decides to discontinue treatment for medical reasons other than nonresponse to study treatment, or due to the patient's significant noncompliance with the protocol.

The reason for termination of study drug before study completion must be recorded in the patient's case report form (CRF). The patient should complete all scheduled study visits provided

CONFIDENTIAL

No use, disclosure, or reproduction outside of Omeros without prior written authorization

written consent to do so has not been withdrawn. Patients who discontinue study drug prematurely will not be replaced.

8.3.2. Patient Withdrawal from the Study

A patient must be withdrawn from the study and discontinue study drug under the following circumstances:

- The patient wishes to withdraw consent to participate in the study.
- The Investigator or patient's primary care provider decides that the patient should be withdrawn from the study.
- The Sponsor decides that the patient should be withdrawn, or the Sponsor discontinues the study for any reason.
- Patient begins prohibited medications that necessitate withdrawal from study.

Prior to patient withdrawal from the study, the Investigator is strongly encouraged to contact the Medical Monitor to discuss withdrawal.

The reason for withdrawal must be recorded in the patient's source documents and CRF. The patient should complete the evaluations scheduled for the Week 96/End-of-Study (EOS) visit, provided written consent to do so has not been withdrawn. Patients who withdraw from the study will not be replaced.

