10.2.6.3. Follow-Up Visit 3 (FU3/EOS) (Weeks 96) ± 14 days

Follow-Up Visit 3/EOS (Week 96) must occur within ± 14 days of the respective target date.

The procedures listed below will be performed and documented for this visit:

- Perform complete physical examination including height and weight. Examination of breast, rectal, and genitourinary systems may be deferred unless clinically necessary
- Collect vital signs including BP, pulse rate, RR, and temperature (all after at least 5 minutes in a seated position)
- Complete ECG after patient has been supine for at least 5 minutes
- Collect urine sample for UA, uPCR, uACR, pregnancy test, and biomarkers (if consent granted by patient for evaluation of optional research biomarkers, aliquot the urine sample as per instructions in the Lab Manual)
- Complete urine pregnancy test

CONFIDENTIAL

No use, disclosure, or reproduction outside of Omertos without prior written authorization

- Collect blood samples for CMP, CBC+diff, ADA, NAb, and biomarkers (if consent granted by patient for evaluation of optional research biomarkers, collect additional blood)
- Assess AEs
- Assess concomitant medications/therapies
- Confirm and document ongoing use of medically acceptable birth control method for patients of childbearing or reproductive potential
- Confirm and document stability of RAS blockade

The procedures below will be performed and documented prior to, during, or after Follow-Up Visit 3/EOS:

- Dispense 24-hour urine collection supplies along with collection instructions to patient. The 24-hour urine collection supplies may be mailed to the patient at any point deemed convenient by the site and patient as long as the supplies are provided in time for the patient to collect the 24-hour urine sample within the required timeframe.
 - At site discretion and for the convenience of the patient, these may be dispensed to the patient at any time during the Follow-Up Period. Patients will have the option to collect the 24-hour urine specimen within 48 hours prior to Follow-Up 3/EOS or within 48 hours after Follow-Up 3/EOS. Patients should be instructed to return the 24-hour urine specimen to the site as soon as possible after its collection. The 24-hour urine collection specimens may be delivered to the study site by the specialty courier service selected by the sponsor, provided the patient has granted consent.
- Collect 24-hour urine sample

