10.2.9. Early Termination

Reasons that patients may discontinue study treatment or withdraw from study participation are detailed in Sections [8.3.1](#) and [8.3.2](#), respectively.

Patients will be encouraged to complete all evaluations. However, provided written consent to do so has not been withdrawn, patients who prematurely discontinue study drug treatment should complete all scheduled study visits, and patients who prematurely discontinue study participation should complete the evaluations scheduled for the FU3/EOS (Week 96) visit. Patients with ongoing SAEs at the time of early termination from the study should be followed for resolution (as possible) or Investigator confirmation that the event is believed to be stable.

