20.2.3. Study Schedule of Events – Response Evaluation and Follow-Up Periods

Period	TC ¹	Response Evaluation Period (Week 13-36)			Follow-Up Period ⁴		
		Week 24	Week 30	Week 36 ^{2,3}	FU1 ⁴ Week 48	FU2 ⁴ Week 72	FU3/EOS ⁵ Week 96
Visit							
Visit window		±7 days	±7 days	±7 days	±14 days	±14 days	±14 days
		TC	TC	9-month visit	1-year visit	1.5-year visit	2-year visit
Complete physical examination ⁶					X		X
Symptom-directed physical examination ⁶				X		X	
Vital signs ⁷				X	X	X	X
ECG ⁶				X	X		X
Dispense 24-hour urine sample supplies ⁸		X	X	X	X	X	X
Collect 24-hour urine sample for UPE, uPCR and uACR ⁹		X	X	X	X	X	X
uPCR and uACR from spot urine ¹⁰				X	X	X	X
Urinalysis ¹⁰				X	X	X	X
Complete blood count with differential ¹⁰				X	X	X	X
Comprehensive metabolic panel ¹⁰				X	X	X	X
Urine pregnancy test ¹¹				X	X	X	X
Biomarker, ADA, and NAb sampling ^{10, 12}				X	X		X
Assess response and need for study drug retreatment ¹³		X	X	X	X	X	X ¹⁴
Adverse events	X	X	X	X	X	X	X
Concomitant medications/therapies	X	X	X	X	X	X	X
Confirm and document stability of RAS blockade				X	X	X	X

Abbreviations: ADA = anti-drug antibody; ECG = electrocardiogram; NAb = neutralizing antibody; PD = pharmacodynamics; PK = pharmacokinetics; RAS = renin-angiotensin system; uACR = urine albumin/creatinine ratio; uPCR = urine protein-to-creatinine ratio; UPE = urine protein excretion

¹ Telephone Calls 1 occur at the following timepoints relative to baseline: Weeks 16, 20, 24, 30, 34, 40, 44, 60, and 84. Assessments for telephone calls for Week 16 through Week 34 must occur within ± 7 days of the target date. Assessments for Telephone Calls for Week 40 through 84 must occur within ± 14 days of the target date.

² RE Week 36 – 9-month visit is the Primary Endpoint

³ During the COVID-19 pandemic: The Response Evaluation Visit/Week 36 (RE/W36) should be conducted at the study site. If this is not possible due to COVID-19 restrictions, the visit may be conducted at the patient's home, or virtually via telephone or video conference if available in the region, if approval has been granted by study site/institution, and if patient provides consent for the service. For specific guidance on how to conduct the RE/W36 visit during the COVID-19 pandemic, refer to Section 10.2.5.

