**Table 1: Estimands For The Primary and Key Secondary Efficacy Endpoints**

Endpoint	Treatment Policy Estimands
Primary	
Primary UPE Endpoint, Patients With Baseline UPE $\geq 2$ g/day	
 
• Treatment regimens to be evaluated = narsoplimab and placebo
 
• The patient population to be evaluated = FAS of all randomized patients with a baseline UPE <math>\geq 2</math> g/day.
 
• The primary UPE endpoint will be analyzed and formally tested for treatment comparison with first 180 patients in the high-risk proteinuria group through 36 weeks in the FAS population.
 
• Patient-level outcome to be analyzed = log change in UPE from baseline to weeks 12, 24, 30 and 36 post randomization, analyzed via mixed model repeated measures analysis (MMRM).
 
• Intercurrent events handling = all patients will be followed for UPE endpoint attainment regardless of early cessation of randomized treatment or the occurrence of intercurrent events such as the use additional systemic therapies.
 
• The population-level estimate of treatment effect = the difference between narsoplimab and placebo in LSmean UPE log change from baseline to 9 months as extracted from the MMRM analysis.
 

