**Table 1: Estimands For The Primary and Key Secondary Efficacy Endpoints (Continued)**

Endpoint	Treatment Policy Estimands
Key Secondary eGFR Endpoint, Patients With Baseline UPE $\geq 2$ g/day	
 
• Treatment regimens to be evaluated = As Primary UPE Endpoint.
 
• The patient population to be evaluated = As Primary UPE Endpoint.
 
• Patient-level outcome to be analyzed = eGFR values collected at 12, 24, 36, 48, 60, 72, 84 and 96 weeks post randomization, analyzed via mixed model repeated measures random coefficients analysis.
 
• Intercurrent events handling = Intercurrent events handling = As Primary UPE Endpoint.
 
• The population-level estimate of treatment effect = the difference between narsoplimab and placebo in eGFR total slope over 96 weeks.
 

Key Secondary eGFR Endpoint, Patients With Baseline UPE $> 1$ g/day	
 
• Treatment regimens to be evaluated = As Primary UPE Endpoint
 
• The patient population to be evaluated = FAS of all randomized patients with a baseline UPE <math>> 1</math> g/day.
 
• Patient-level outcome to be analyzed = eGFR values collected at 12, 24, 36, 48, 60, 72, 84, and 96 weeks post randomization, analyzed via mixed model repeated measures random coefficients analysis.
 
• Intercurrent events handling = As Primary UPE Endpoint.
 
• The population-level estimate of treatment effect = the difference between narsoplimab and placebo in eGFR total slope over 96 weeks.
 

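### Protocol 8.3.2 can end follow-up when a patient starts an unnamed prohibited medicine, against the treatment-policy follow-up in SAP Table 1

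*Protocol*

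**What the plan says.** Protocol 8.3.2 lists circumstances in which a patient must leave the study and stop study drug. One of them reads "Patient begins prohibited medications that necessitate withdrawal from study". It gives no list and no cross-reference. Section 10.4 prohibits, among others, Tarpeyo and other approved IgAN treatments, finerenone and newly started SGLT2 inhibitors, but does not say which of these lead to withdrawal.

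For a withdrawn patient, 8.3.2 says: "The patient should complete the evaluations scheduled for the Week 96/End-of-Study (EOS) visit, provided written consent to do so has not been withdrawn". Section 10.2.9 agrees: "patients who prematurely discontinue study participation should complete the evaluations scheduled for the FU3/EOS (Week 96) visit". Neither says whether this happens at withdrawal or at Week 96. Two softer sentences belong beside these. Section 10.2.9 opens by encouraging patients to complete all evaluations, and 8.3.2 strongly encourages contact with the Medical Monitor before a withdrawal.

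SAP Table 1 sets treatment-policy estimands. Its rule for the primary endpoint, whose one example is added systemic therapy, reads "all patients will be followed for UPE endpoint attainment regardless of early cessation of randomized treatment or the occurrence of intercurrent events such as". For each key secondary eGFR endpoint it repeats: "Intercurrent events handling = As Primary UPE Endpoint".

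**The concern.** Starting another therapy is the kind of intercurrent event that Table 1 says will not stop follow-up. If the bullet is applied, the scheduled UPE and creatinine values after that event are not collected. The MMRM and the random-coefficients slope model then rely on missing-at-random for those patients, in place of the observed outcomes the estimand calls for.

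Because the bullet names no medicine, two sites could treat the same patient differently. One could end follow-up and the other continue it.

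The planned sensitivity analyses (SAP 2.9.2.2, applied to eGFR by 2.9.2.3) impute from placebo data or add a penalty to narsoplimab patients. They test robustness to missing data, but they do not recover outcomes under the added medicine.

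**Working it through.** **The rules side by side**

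| Situation | Study drug | Follow-up | Source |
|---|---|---|---|
| Stops study drug only | Stopped | All scheduled visits | Protocol 8.3.1 |
| Rescue therapy | Stopped | Continues through the Follow-Up Period | Protocol 10.4.1 |
| Prohibited medicine judged to require withdrawal | Stopped | EOS evaluations only | Protocol 8.3.2, 10.2.9 |
| Additional systemic therapy | – | All patients followed | SAP Table 1 |

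Only the third row disagrees with the fourth. The EOS set is not empty. It includes a 24-hour urine and, at FU3/EOS, "Collect blood samples for CMP, CBC+diff, ADA, NAb, and biomarkers", so one further UPE and one further creatinine value. In the Schedule of Events (20.2.3), the row "Comprehensive metabolic panel" is marked at Weeks 36, 48, 72 and 96, so up to two scheduled creatinine values between Week 36 and Week 96 are lost even if the EOS set is taken at Week 96.

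**Plan's own figure.** The inputs are residual variance 42.3499 and monthly slope variance 0.5411 (SAP Appendix 3), Sxx = 378 and an effect of 3.48 mL/min/year (SAP 1.3.2).

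N = 4(1.960 + 1.036)² / (3.48/12)² × (42.3499/378 + 0.5411) = 278.9, against the stated 280. At N = 280, SE = 12 × √(4/(280 × 1.531)) = 1.159 and power = Φ(3.48/1.159 − 1.96) = 85.1%.

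**Information lost per withdrawn patient.** Slope information per patient is 1/(42.3499/Sxx + 0.5411). Three schedules are used, in months:

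- A, SAP sizing: 3, 6, …, 24. Sxx = 378, information 1.531, power 85.1%.
- B, protocol creatinine visits: 0, 1, 2, 3, 9, 12, 18, 24. Sxx = 543.875, information 1.616, SE 1.128, power 86.9%.
- C, only those Table 1 weeks at which the protocol schedules creatinine for everyone (12, 36, 48, 72, 96): 3, 9, 12, 18, 24. Sxx = 262.8, information 1.424, SE 1.202, power 82.5%.

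For withdrawal after month 9, the remaining Sxx, the loss, and the power if an assumed 20% of patients are affected (mean information × (1 − 0.20 × loss)) are:

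| Schedule | No EOS value | EOS value 6 weeks later | EOS value at Week 96 |
|---|---|---|---|
| A | Sxx 18, loss 77%, power 78.8% | 33.19, 64%, 80.0% | 261, 7%, 84.6% |
| B | 50, 55%, 82.8% | 96.88, 37%, 84.3% | 417.5, 4%, 86.7% |
| C | 18, 76%, 76.0% | 31.5, 63%, 77.3% | 234, 3%, 82.3% |

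Example for A: 1/(42.3499/18 + 0.5411) = 0.346; loss = 1 − 0.346/1.531 = 0.774; factor 1 − 0.20 × 0.774 = 0.845; power 78.8%.

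At an assumed 5% or 10% with no EOS value, power is 83.7% or 82.2% on A, and 86.0% or 85.0% on B. Later withdrawal costs less. With no EOS value the loss is 56% (A) or 31% (B) after month 12, and 19% or 11% after month 18.

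**Bias illustration, schedule B, no EOS value.** Suppose withdrawal is more frequent on placebo by 5 to 15 percentage points, and the added medicine would improve slope after Week 36 by 1 to 3.48 mL/min/year. The share of that gain reaching the total slope is f = Σ(t − 8.625) × max(t − 9, 0)/543.875 = (10.125 + 84.375 + 230.625)/543.875 = 0.598. Overstatement runs from 0.05 × 1 × 0.598 = 0.03 to 0.15 × 3.48 × 0.598 = 0.31 mL/min/year, or up to 0.28 of the SE of 1.128. This assumes a common slope before withdrawal within each arm.

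**The case against.** The best counter-argument is that nothing shows the rule in operation. The bullet is conditional, no medicine is tied to it, and a Medical Monitor consulted beforehand could read it as covering nobody. The main routes to an added therapy, stopping study drug and rescue, already keep follow-up, and 10.2.9 encourages complete evaluations. The losses rest on assumed rates, and the largest ones assume no EOS value although the protocol asks for one. The tipping-point analysis goes as far as full reversal of the effect in narsoplimab patients with missing data.

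Most of this stands, and it limits the size and reach of the point. It does not remove the conflict: where the bullet is applied, the protocol asks for less than Table 1 promises. A penalty on narsoplimab patients also says little if the missing patients are mainly on placebo.

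Three stronger readings are tempting and not supported:

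- That every patient who starts a section 10.4 medicine is lost. The conditional wording does not say so.
- That the slope effect will be overstated. This needs more withdrawals on placebo and an added medicine that slows eGFR decline; the documents establish neither.
- That half the slope information is at risk. The SAP information fraction of 49.1% (52.591/107.175) leaves 50.9% still to come from all patients. This shows there is time to act; it does not measure what the bullet could remove.

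**Conclusion.** The point holds as a conflict between a conduct rule and the declared estimands, for the primary and both eGFR endpoints, limited to patients withdrawn under this bullet outside rescue. How many there will be is unknown and may be zero.

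The power and bias figures are illustrations under assumed rates, timing and schedule. They are not bounds: the 20% case with no EOS value costs 6.3 points on schedule A (85.1 − 78.8), 4.1 on B (86.9 − 82.8) and 6.5 on C (82.5 − 76.0), and a higher rate would cost more. EOS timing matters more than the choice of schedule. A value at Week 96 reduces the per-patient loss after month 9 to 3–7%.

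SAP 2.9.7 describes recruitment of the first 180 high-risk patients in the past tense, so a change now does little for the primary UPE analysis. The benefit is to eGFR slope. It is worth fixing because uncollected values cannot be recovered later and the correction is small.

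**What to change.** - Delete the prohibited-medication bullet from 8.3.2.
- State in 10.4 that starting a prohibited medicine is recorded with dates and is not in itself a reason to end follow-up.
- If study drug is stopped, handle the patient under 8.3.1 and keep all scheduled UPE and creatinine visits through Week 96 unless consent is withdrawn.
- Leave the consent, Investigator, primary care provider and Sponsor bullets of 8.3.2 unchanged. They serve clinical judgement and are not the defect.
- The same amendment can usefully say when the EOS evaluations are done for patients withdrawn under those remaining bullets.

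The cost is amendment text, with IRB/IEC approval before implementation (Protocol 17.1) at about 200 sites, and at most three more scheduled visits (Weeks 48, 72 and 96) per affected patient after Week 36. Until approval, written Medical Monitor guidance that no section 10.4 medicine requires study withdrawal fits the conditional wording. The sponsor should also accept that including outcomes under an added medicine may make the estimated effect smaller; that is what a treatment-policy estimand measures.
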